2.4.5 Safety Profile

Refer to the Investigator's Brochure (IB) for Pharmacokinetic data.

Most common adverse reactions ($\geq 20\%$) in patients treated with nivolumab as monotherapy, included fatigue, rash, musculoskeletal pain, pruritus, diarrhea, nausea, asthenia, cough, dyspnea, constipation, decreased appetite, back pain, arthralgia, upper respiratory tract infection, pyrexia. In combination with ipilimumab, the most common reactions were fatigue, rash, diarrhea, nausea, pyrexia, vomiting, and dyspnea.

Nivolumab should be withheld for moderate and permanently discontinued for any of the following serious or life-threatening adverse reactions: pneumonitis, colitis, hepatitis (transaminase or total bilirubin elevation), nephritis and renal dysfunction, hypophysitis, adrenal insufficiency, encephalitis, or infusion reactions.

Patients with prior allogeneic HSCT should be monitored for signs of hyperacute, grade 3-4 acute GVHD, steroid-requiring febrile syndrome, hepatic veno-occlusive disease, and other immunemediated adverse reactions. Transplant-related mortality has occurred. Nivolumab can cause fetal harm.

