6. DOSING DELAYS/DOSE MODIFICATIONS

The descriptions and grading scales found in the revised NCI Common Terminology Criteria for Adverse Events (CTCAE) version 4.0 will be utilized for dose delays and dose modifications for nivolumab and ipilimumab.

Patients with Grade 3-4 scalp skin toxicity from NovoTTF200A (OptuneTM) application, should hold TTFields therapy until resolved to Grade ≤ 2 , then resume at same compliance goal of 75% or above. Interval maximal topical or systemic therapy advised. Repositioning of arrays is advised for any Grade ≤ 2 along with maximal medical therapy.

Adverse events (both non-serious and serious) associated with nivolumab and/or ipilimumab exposure may represent an immunologic etiology. These adverse events may occur shortly after the first dose or several months after the last dose of treatment. Immunotherapy must be withheld for drug-related toxicities and severe or life threatening toxicities. See Section 5.5.1 for supportive care guidelines, including use of corticosteroids.

Criteria for disrupting treatment, dose modification, or discontinuation for adverse events that are attributable to nivolumab or ipilimumab are listed below. After dose modifications are per the clinical judgment of the investigator and agreement of the subject, the treatment will be resumed according to the table below. Dose modification may not be required for adverse events that are clinically manageable.

Toxicity	Hold For Grade	Timing for Restarting Treatment	Treatment Discontinuation
Diarrhea/ Colitis	2-3	Toxicity resolves to Grade 0-1	Toxicity does not resolve within 12 weeks of last dose or inability to reduce corticosteroid to 10 mg or less of prednisone or equivalent per day within 12 weeks
	4	Permanently discontinue	Permanently discontinue
AST, ALT, or	2	Toxicity resolves to Grade 0-1	Toxicity does not resolve within 12 weeks of last dose
High Bili ru bin	3-4	Permanently discontinue (see exception below)	Permanently discontinue
Type 1 diabetes mellitus (new onset) or Hyperglycemia	T1DM or 3-4	Hold immunotherapy for new onset Type 1 diabetes mellitus or Grade 3-4 hyperglycemia associated with evidence of beta cell failure	Resume immunotherapy when patients are clinically and metabolically stable

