Hypophysitis	2-4	Toxicity resolves to Grade 0-1. Therapy with immunotherapy can be continued while endocrine replacement therapy is instituted	Toxicity does not resolve within 12 weeks of last dose or inability to reduce corticosteroid to 10 mg or less of prednisone or equivalent per day within 12 weeks

Dose Modification Guidelines for Drug-Related Adverse Events

Toxicity	Hold For Grade	Timing for Restarting Treatment	Treatment Discontinuation
Hyperthyroidism	3	Toxicity resolves to Grade 0-1	Toxicity does not resolve within 12 weeks of last dose or inability to reduce corticosteroid to 10 mg or less of prednisone or equivalent per day within 12 weeks
	4	Permanently discontinue	Permanently discontinue
Hypothyroidism		Therapy with immunotherapy can be continued while thyroid replacement therapy is instituted	Therapy with immunotherapy can be continued while thyroid replacement therapy is instituted
Infusion Reaction	2ª	Toxicity resolves to Grade 0-1	Permanently discontinue if toxicity develops despite adequate premedication
	3-4	Permanently discontinue	Permanently discontinue
Pneumonitis	2	Toxicity resolves to Grade 0-1	Toxicity does not resolve within 12 weeks of last dose or inability to reduce corticosteroid to 10 mg or less of prednisone or equivalent per day within 12 weeks
	3-4	Permanently discontinue	Permanently discontinue
Renal Failure or Nephritis	2	Toxicity resolves to Grade 0-1	Toxicity does not resolve within 12 weeks of last dose or inability to reduce corticosteroid to 10 mg or less of prednisone or equivalent per day within 12 weeks
	3-4	Permanently discontinue	Permanently discontinue
All Other Drug- Related Toxicity ^b	3 or Severe	Toxicity resolves to Grade 0-1	Toxicity does not resolve within 12 weeks of last dose or inability to reduce corticosteroid to 10 mg or less of prednisone or equivalent per day within 12 weeks
	4	Permanently discontinue	Permanently discontinue

Note: Permanently discontinue for any severe or Grade 3 drug-related AE that recurs or any lifethreatening event.

^a If symptoms resolve within one hour of stopping drug infusion, the infusion may be restarted at 50% of the original infusion rate (e.g., from 100 mL/hr to 50 mL/hr). Otherwise dosing will be held until symptoms resolve and the subject should be premedicated for the next scheduled dose; Refer to Investigator's Brochure (IB) – Infusion Treatment Guidelines for further management details.

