^b Patients with intolerable or persistent Grade 2 drug-related AE may hold study medication at physician discretion. Permanently discontinue study drug for persistent Grade 2 adverse reactions for which treatment with study drug has been held, that do not recover to Grade 0-1 within 12 weeks of the last dose

If a patient experiences other adverse events, or several adverse events and there are conflicting recommendations based on Grade, the investigator will use the lowest reduced the dose. Dose modifications will be made based on an adverse event that occurs during any time during a cycle.

Participants who experience an adverse event that requires a treatment delay or dose reduction should be monitored with appropriate laboratory testing or other clinical evaluation at least weekly until resolution; if the adverse event does not resolve within 12 weeks, the Investigator will determine the best course of action.

For holds for reasons other than treatment related toxicities, if the participant does not meet criteria to resume treatment within 6 weeks of the event precipitating the hold, the study agent(s) may be restarted, as long as there has been no significant evidence of disease progression (e.g., by clinical findings, symptoms, tumor markers) during the treatment interruption.

Dosing interruptions are permitted in the case of medical / surgical events or logistical reasons not related to study therapy (e.g., elective surgery, unrelated medical events, patient vacation, and/or holidays). Subjects should be placed back on study therapy within 3 weeks of the scheduled interruption, unless otherwise discussed with the Sponsor. The reason for interruption should be documented in the patient's study record.

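### The section 6 dosing table has no Grade 2 hold for two of the eight reactions named in section 2.4.5: encephalitis and adrenal insufficiency

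*Combined protocol and SAP*

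**What the plan says.** Section 2.4.5 states: "Nivolumab should be withheld for moderate and permanently discontinued for any of the following serious or life-threatening adverse reactions". Its list begins with pneumonitis, colitis, hepatitis and nephritis, and ends with "hypophysitis, adrenal insufficiency, encephalitis, or infusion reactions". Section 2.5.4 says much the same for ipilimumab: moderate immune-mediated toxicity calls for a hold or delay.

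Section 5.1 sends the reader to section 6 for dose modifications, and section 6 introduces its table with: "Criteria for disrupting treatment, dose modification, or discontinuation for adverse events that are attributable to nivolumab or ipilimumab are listed below". Neither encephalitis nor adrenal insufficiency appears there by name. The row that would take them is "All Other Drug- Related Toxicity", which holds at Grade 3 or severe, allows restart at Grade 0-1, and discontinues permanently at Grade 4. A note under the table adds permanent discontinuation for a severe or Grade 3 event that recurs. Footnote b covers Grade 2: "Patients with intolerable or persistent Grade 2 drug-related AE may hold study medication at physician discretion".

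The text before the table contains two general sentences that pull in different directions: "Immunotherapy must be withheld for drug-related toxicities and severe or life threatening toxicities" and "Dose modification may not be required for adverse events that are clinically manageable".

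**The concern.** The two safety summaries point to a hold at moderate severity. For these two reactions the table makes a Grade 2 hold optional, and only when the event is intolerable or persistent. A site working from the table could give the next infusion during a Grade 2 event of either type and reasonably believe that it was following the protocol.

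The same missing rows create a second mismatch at Grade 3. Section 2.4.5 calls for permanent discontinuation when the reaction is serious, while the catch-all row lets a first Grade 3 event restart after it resolves.

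What is at stake is patient safety and consistent conduct between sites. The primary endpoint is not affected.

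**Working it through.** No sample size or error rate is involved. The check matches each reaction in section 2.4.5 to a row of the section 6 table and reads the grade at which the hold starts.

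| Reaction in 2.4.5 | Row in section 6 | Hold grade |
|---|---|---|
| Pneumonitis | Pneumonitis | 2 |
| Colitis | Diarrhea/colitis | 2-3 |
| Hepatitis | AST, ALT or bilirubin | 2 |
| Nephritis, renal dysfunction | Renal failure or nephritis | 2 |
| Hypophysitis | Hypophysitis | 2-4 |
| Infusion reactions | Infusion reaction | 2 |
| Adrenal insufficiency | none (catch-all) | 3 or severe |
| Encephalitis | none (catch-all) | 3 or severe |

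Named reactions: 8. With Grade 2 in the hold: 6. Without: 8 - 6 = 2, or 2/8 = 25% of the list.

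**Meaning of moderate.** Section 2.4.5 gives no grade. Section 2.2.3 pairs mild to moderate with Grades 1 and 2 when it describes scalp dermatitis, so reading moderate as Grade 2 fits the protocol's own usage. It remains an inference.

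**Does other text supply the missing rule?**

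- The general sentence that immunotherapy must be withheld carries no grade. Read literally it contradicts the table, which continues dosing in hypothyroidism and holds hyperthyroidism only from Grade 3. It makes the position ambiguous but sets no Grade 2 rule.
- Section 5.5.1 has no supportive care entry for either event. It refers to Appendices E and F.
- For adrenal insufficiency, the Appendix E endocrine algorithm delays therapy for symptomatic endocrinopathy with an abnormal laboratory result or pituitary scan, and delays or stops it for suspected adrenal crisis. Both instructions are ungraded and refer back to the protocol. The section 10 calendar tests cortisol and ACTH at treatment visits and uses the results to clear the next infusion. That detects the event but does not say when to hold. The hypophysitis row says "Therapy with immunotherapy can be continued while endocrine replacement therapy is instituted", so a matching adrenal row would also allow dosing on replacement. The practical gap is small.
- For encephalitis, Appendices E and F each contain a neurological algorithm, but the available text shows no decision content for either. They may or may not call for a delay at Grade 2.

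**The case against.** Section 2.4.5 is background, its sentence is garbled, and the list grammatically follows the serious or life-threatening clause. Section 6 departs from it elsewhere: Grade 3 colitis may restart, and hypophysitis is held through Grade 4 with dosing allowed on replacement. The section 6 table is itself titled as guidelines and leaves room for investigator judgment, so Appendix E cannot be dismissed merely because it calls itself guidance. On this view the adrenal case is largely handled, the encephalitis case cannot be verified, and the remainder is editorial.

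Much of this stands. It limits the practical consequence, and it rules out treating section 2.4.5 as a binding dosing rule that section 6 breaches. It does not remove the mismatch. Section 2.5.4 independently calls for a hold at moderate severity. The Appendix E endocrine instructions refer back to the protocol for the decision. The table already applies a Grade 2 hold to the other six reactions on the same list, and the documents give no reason for treating these two differently.

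A reader might go further and infer three things that the documents do not support:

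- That the protocol plainly permits dosing through Grade 2 encephalitis. The general withholding sentence and the neurological algorithms that are not shown leave this open.
- That extra exposure is capped at one 6-week cycle (3 nivolumab infusions and 1 ipilimumab dose). Nothing limits an unheld event to one cycle, and the 12-week stop in footnote b applies only once treatment has been held.
- That 25% describes patients at risk. It is a share of listed reactions, and no incidence is given for either event.

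**Conclusion.** The point holds as an internal inconsistency. Two of the eight reactions in section 2.4.5 have no Grade 2 hold in section 6, and for a first Grade 3 event the table allows a restart where section 2.4.5 points to permanent discontinuation. This rests on two assumptions: that moderate means Grade 2, and that an event without its own row falls under the catch-all.

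For adrenal insufficiency the consequence in practice is small. For encephalitis it is conditional on the neurological algorithms, although the table fails to match section 2.4.5 whatever they say. No patient count, dosing ceiling or endpoint effect is claimed. This is a cheap safety improvement worth considering, not a flaw that threatens the trial's conclusions.

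**What to change.** Add two full rows to the section 6 table and except both events from footnote b.

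- **Encephalitis:** hold nivolumab and ipilimumab at Grade 2 until Grade 0-1. Discontinue permanently at Grade 3-4, in line with section 2.4.5. Check the row against the neurological algorithms in Appendices E and F before it is finalized.
- **Adrenal insufficiency:** hold both drugs at Grade 2 until Grade 0-1, with dosing allowed on stable hormone replacement, as in the hypophysitis row. Keep at least the present catch-all rules: hold at Grade 3, discontinue permanently at Grade 4.

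The rows must cover Grades 3 and 4. Moving the events out of the catch-all with a Grade 2 rule alone would drop the hold and discontinuation rules that now apply to them. For the same reason, each row should carry its own 12-week non-resolution condition.

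The cost is two table rows and one footnote exception in an amendment, with no new visits, data or analyses. The downside is a few more dose holds or discontinuations.

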5.8 Criteria for Taking a Participant off Protocol Therapy

Duration of therapy will depend on individual response, evidence of disease progression and tolerance. Treatment will be discontinued for clinical or radiographic progression of disease, intolerance despite dose modification (defined as NCI Common Terminology Criteria for Adverse Events (CTCAE) version 4.0 Grade 3 or 4 that does not return to Grade 1 or 2 after interruption or reduction of dose for 4 weeks), or patient withdrawal. A patient who experiences a dose-limiting toxicity (DLT) can remain on study at a reduced dose, if deemed by the physician to be safe and beneficial for the patient to continue.

In the absence of treatment delays due to adverse events, treatment may continue until one of the following criteria applies:

- Global deterioration of health-related symptoms (clinical progression),
- Confirmed radiographic disease progression,

- Intercurrent illness that prevents further administration of treatment,
- Unacceptable adverse event(s),
- Treatment interruption for more than 4 consecutive weeks due to intolerance despite appropriate dose modification,
- Participant decides to withdraw from the study, or
- General or specific changes in the participant's condition render the participant unacceptable for further treatment in the opinion of the treating investigator,
- Protocol non-compliance,
- Pregnancy,
- Lost to follow-up, or
- Study termination by Investigator, Institution or IRB.

If a patient does not return for a scheduled visit, every effort should be made to contact the patient. In any circumstance, every effort should be made to document patient outcome, if possible. The Investigator should inquire about the reason for withdrawal, request that all unused investigational product(s) be returned, request the patient to return for a final visit, if applicable, and advise follow-up with the patient regarding any unresolved adverse events.

If the patient withdraws from the trial and also withdraws consent for disclosure of future information, then no further evaluations should be performed and no additional data should be collected. The Investigator may retain and continue to use any data collected before such withdrawal of consent.

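### Sections 5.8 and 6 rely on a reduced dose that the dose-modification table never gives, and they set different time limits (4 versus 12 weeks) for toxicity that stays at Grade 3-4

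*Combined protocol and SAP*

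**What the plan says.** Section 5.1 sends the reader to section 6 for dose modifications. Section 6 leaves modifications to clinical judgment and the patient's agreement, after which "the treatment will be resumed according to the table below". The table has columns for the grade at which to hold, the timing of restart, and discontinuation. Most holds end in restart at Grade 0-1. For diarrhea/colitis at Grade 2-3 the discontinuation entry reads "Toxicity does not resolve within 12 weeks of last dose or inability to reduce corticosteroid to 10 mg or less" (a daily prednisone-equivalent dose). The hypophysitis row (Grade 2-4) adds: "Therapy with immunotherapy can be continued while endocrine replacement therapy is instituted". A note under the table says: "Permanently discontinue for any severe or Grade 3 drug-related AE that recurs or any lifethreatening event".

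After the table, where several events lead to conflicting recommendations, "the investigator will use the lowest reduced the dose". The next paragraph again mentions dose reduction as a possible action, and leaves an event unresolved at 12 weeks to the investigator.

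Section 5.8 sets its own rules. Intolerance despite dose modification is "Grade 3 or 4 that does not return to Grade 1 or 2 after interruption or reduction of dose for 4 weeks". The list of stopping criteria includes "Treatment interruption for more than 4 consecutive weeks due to intolerance despite appropriate dose modification". A patient with a DLT "can remain on study at a reduced dose, if deemed by the physician to be safe and beneficial".

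**The concern.** These rules decide whether a patient with immune-related toxicity stays on checkpoint inhibitors. If the conflict rule points to an action that the table does not contain, it settles nothing. If the DLT sentence carries no exception, it can be read as permitting what section 6 forbids. If the two sections give different times for stopping, two investigators can treat the same unresolved Grade 3 event differently, and both can cite the protocol. The rates and reasons of discontinuation are also a secondary objective (section 1.3) and are to be reported under section 13.4, so that summary would partly depend on which section each investigator followed.

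**Working it through.** No sample-size or error-rate arithmetic applies. The check is a count of the section 6 table and a side-by-side reading with section 5.8.

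**Step 1. Is there a reduced dose to choose?** Grade rows by category: diarrhea/colitis 2, AST/ALT/bilirubin 2, type 1 diabetes or hyperglycemia 1, hypophysitis 1, hyperthyroidism 2, hypothyroidism 1, infusion reaction 2, pneumonitis 2, renal 2, all other 2. The total is 17. By action:

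| Action | Rows |
|---|---|
| Hold and restart only | 8 |
| Hold and restart, continuation also allowed (hypophysitis) | 1 |
| Permanent discontinuation (hepatic row has an exception that cannot be read) | 7 |
| Continue only (hypothyroidism) | 1 |
| Reduced dose | 0 |

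8 + 1 + 7 + 1 = 17. The only 50% figure (footnote a) halves the infusion rate, not the dose. Section 2.4.5 also speaks only of withholding or permanently discontinuing nivolumab.

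**Step 2. Does the conflict rule work?** Take Grade 3 pneumonitis (discontinue) together with Grade 2 diarrhea (hold). The choice is between two actions, and a reduced dose is neither. The wording is garbled and the intent is probably the most cautious action, but the sentence does not say so.

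**Step 3. The DLT sentence.** DLT is not defined in the text available. The sentence requires the physician to judge continuation safe and beneficial, but it exempts neither the 7 discontinuation rows nor the note on recurrent Grade 3 and life-threatening events. It conflicts with section 6 whenever such an event is called a DLT.

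**Step 4. Which rows have two time limits?** Seven hold rows carry the 12-week limit: diarrhea/colitis 2-3, hepatic 2, hypophysitis 2-4, hyperthyroidism 3, pneumonitis 2, renal 2, all other 3. The section 5.8 definition concerns Grade 3-4, which leaves four:

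- Diarrhea/colitis Grade 3, hyperthyroidism Grade 3 and all other Grade 3 are clear. Colitis still at Grade 3 in week 5 is off therapy under section 5.8 and on a permitted hold under section 6.
- Hypophysitis is arguable. The row lets immunotherapy continue during hormone replacement, so there may be no interruption to time, and the note on life-threatening events may remove Grade 4 from the hold.

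**Step 5. How far apart are the limits?** The table counts from the last dose. Section 5.8 does not say where its 4 weeks start, so the start is an assumption:

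- From the last dose: 12 − 4 = 8 weeks, or 8/2 = 4 two-weekly nivolumab slots.
- From the first missed two-weekly dose: 12 − (2 + 4) = 6 weeks, or 6/2 = 3 slots.

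A different start would give a gap outside this range.

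**Step 6. Section 6 at 12 weeks.** The table, and footnote b for persistent Grade 2 events, require discontinuation. The later paragraph hands the same situation to the investigator.

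**The case against.** The strongest reply is that section 6 governs. Section 5.1 names it for dose modifications, the list in section 5.8 is introduced as applying when there are no delays for adverse events, and its interruption item presupposes appropriate dose modification. This has some force, but section 5.1 is a pointer and not a rule of precedence. The lead-in is also hard to square with a list item that is itself about interruption for intolerance.

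A second reply is that clinical judgment fills the gap. Judgment supplies no dose level, and it does not reconcile 4 weeks with 12.

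A third is that some material cannot be seen: the hepatic exception, most of the Appendix E and F figures, and the Investigator's Brochure. The claim about doses is therefore limited to the readable text. The difference in time limits needs none of that material.

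Three stronger readings are tempting, and the documents do not support them:

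- A reader might infer that section 5.8 is looser on grade because it asks for Grade 1 or 2 where the table asks for 0-1. The first is a test for coming off therapy and the second a condition for restart. They can be followed in sequence: at Grade 2 in week 4 the patient stays on hold, and restarts only at Grade 0-1.
- A reader might infer that the Grade 2 rows with a 12-week limit conflict as well, through the item on interruptions over 4 weeks. That item applies to intolerance, which section 5.8 has just defined by unresolved Grade 3-4 toxicity.
- A reader might infer that Grade 3-4 pneumonitis or nephritis has no controlling instruction. The table's mandate to discontinue stays in force.

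**Conclusion.** The point holds as a minor one: rules on treatment safety that are wrong as written. Two sentences invoke a reduced dose that 0 of 17 rows provide, and one of them lacks an exception for mandatory discontinuation. For toxicity that persists at Grade 3-4, sections 5.8 and 6 set different limits in three clear rows and one arguable row, 6 to 8 weeks apart under the two assumed clock starts. Under either section the drug is withheld while the toxicity persists. What differs is whether the patient is already off therapy or may still restart. The number of patients affected cannot be estimated from the documents. Nothing here changes alpha, power, sample size or the response-rate decision rule.

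**What to change.** Four changes in one amendment:

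1. In section 6, replace the conflict clause with a rule that the most conservative action in the table applies: discontinue over hold, hold over continue.
2. In section 5.8, delete the DLT sentence or make it expressly subject to the permanent-discontinuation rules of section 6. Remove the remaining mentions of dose reduction in both sections unless a reduced level is defined for each drug.
3. State one time limit for persistent Grade 3-4 toxicity in both sections, and say when its clock starts. The choice between 4 and 12 weeks is clinical and belongs to the sponsor. Moving to 12 weeks would loosen a stricter stop, so keep 4 unless 12 was intended. Keep Grade 0-1 for restart where the table requires it.
4. In section 6, for drug-related events unresolved at 12 weeks, replace the investigator's discretion with the table's discontinuation rule.

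The cost is amendment wording plus one clinical decision, and possibly a few more early discontinuations. Sample size, visits and analyses do not change.
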